**Table 1-1. Schedule of Activities**

	SCR a	Treatment Period (21-day Cycles) b								EoT d	STFU e	LTFU f	Notes	
		D1	D3	D5	D8	D10	D12	D15 c	D16-21					
B-cells and immunophenotype	X	X					(X)			X	X		(X): Day 12 of Cycle 1 only	
Complement	X	X								X			Should be assessed before the start of infusion and 3 hours after the start of infusion ( $\pm$ 10 min), or if a subject experiences a Grade $\geq$ 2 IRR/CLS/CRS or other hypersensitivity reaction. See Section 10.2.2.3 for details.	
Histamine	X	X								X				
Cytokines	X	X								X				
Immunoglobulins	X	X								X			Should be assessed before the start of infusion and 3 hours after the start of infusion ( $\pm$ 10 min).	
Optional tumor tissue biopsy										X			Applicable to subjects who had consented for this procedure, exhibit PD, and have accessible peripheral lymph node(s).	
Efficacy Assessments														
Radiological assessment	X	Every 6 weeks ( $\pm$ 1 week) starting from C1D1, until disease progression, death, or lost to follow-up AND For subjects without response or SD at EoT: within 7 days of the EoT Visit ( only if the previous tumor scan has been performed $>$ 4 weeks before the EoT Visit)								The investigator is encouraged to obtain the screening tumor scan as close as possible to the start of treatment. The original schedule needs to be maintained even if there is a delay in dosing. Subjects who continue to receive treatment beyond progression should also have repeat scans.				
EQ-5D	X	(X)								X	X		(X): Collected D1 of every even cycle (C2, C4, C6, etc)	
Study Treatment														
Premedication		X	X	X	X	X	X	(X)					Administered within 60 minutes prior to MT-3724 infusion. Refer to Section 6.1.2 for guidance. (X): Only when weekly dosing is implemented.	
MT-3724 infusion (TIW)		X	X	X	X	X	X						The first 3 doses of Cycle 1 must be administered at least 2 days (approx. 48 hours) apart. All subsequent doses must be given within $\pm$ 1 day of scheduled visit. All 6 doses must be given within the first 16 days, the doses should be at least 20 hours apart, and should not be administered on more than 2 consecutive days.	
MT-3724 infusion (weekly schedule) h		X			X			X					Starting with Cycle 3, doses will be administered weekly. Doses must be given within $\pm$ 2 day of scheduled visit.	

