The DLT assessment period is 21 days. DLTs will be assessed during Cycle 1 of each enrolled dose cohort.

Starting with enrollment into Cohort 1, a minimum of 6 eligible subjects will be enrolled into 1 of 2 predefined sequential dose cohorts, unless precluded by DLTs. Each dose cohort is deemed intolerable if 2 or more DLTs occur at any time in Cycle 1.

If permitted by the safety results, the MT-3724 dose escalation is planned to proceed in sequential dose cohorts. Before each dose escalation decision, the sponsor, investigators and independent pharmacovigilance physician will review all available data in the current dose cohort. The safety management team must decide by consensus whether it is safe to proceed to the next planned dose level, or to another dose not pre-specified in the protocol.

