#### **4.1.1.1      Subject Evaluable for Dose Decisions**

Subjects in Part 3 will be evaluable for dose decisions if they satisfy one of the following criteria:

- Have had a DLT after at least one dose of MT-3724 in Cycle 1; or
- In the absence of toxicities that have delayed or caused omission of doses, subjects have received at least 4 of 6 (67%) doses of MT-3724 within 21 days

Subjects who are not evaluable for dose decisions will be replaced.

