### **Cohort 2:**

The starting MT-3724 dose in each subject will be 10 µg/kg for the first 2 doses (D1, D3). The dose will then be increased to 25 µg/kg for 2 doses (D5, D8) and then the dose will be increased to 50 µg/kg for the remaining doses (D10, D12) of the first 21-day cycle and all doses of Cycle 2. Dosing will then continue at 50 µg/kg weekly (D1, D8, D15) beginning with Cycle 3 ([Table 6-1](#)).

If fewer than 2/6 subjects have a DLT in Cohort 2, then the study will continue to Part 4 using the Cohort 2 dose and schedule. If 2 / 6 subjects experience a DLT in Cohort 2, the study will continue to Part 4 using the Cohort 1 dose and schedule.

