**Table 6-1. Step-up Dosing Schedule for Cohorts 1 and 2**

Day	MT-3724 Dose (µg/kg) a,b	
	Cohort 1 (n = 6)	Cohort 2 (n = 6)
Cycle 1 D1, D3	10	10
Cycle 1 D5, D8	25	25
Cycle 1 D10, D12	25	50
Cycle 2 D1, D3, D5, D8, D10, D12	25	50
Cycle 3+ D1, 8, 15 (weekly dosing)	25	50

a The total administered dose of MT-3724 must not exceed 1200 µg per infusion for the 10 µg/kg dose; 3000 µg per infusion for the 25 µg/kg dose and 6000 µg per infusion for the 50 µg/kg dose in all treatment cycles.

b Each dose of MT-3724 must be preceded by premedication administered within 60 minutes before the start of each infusion (see [Section 6.1.2](#)).

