##### **6.1.1.3 Dose Schedule**

All doses of MT-3724 will be administered as IV infusion over 1 hour (window = 54 to 75 minutes) in a 21-day cycle according to the schedule specified in each cohort ([Table 6-1](#)).

NOTE: Each dose of MT-3724 must be preceded by premedication administered within 60 minutes before the start of each infusion (see [Section 6.1.2](#))

All doses should be administered within the first 16 days of the 21-day cycle. For Cycle 1 and 2 doses are preferably administered on Days 1, 3, 5, 8, 10, and 12 ( $\pm 1$  d). For Cycle 3 and later doses are preferably administered on Days 1, 8, and 15. All cycles should use the following guidelines:

- The first 3 doses of Cycle 1 must be administered at least 2 days (approximately 48 hours) apart.
- All subsequent doses must be at least 20 hours apart (more than 5 half-lives of MT-3724 in serum), and must not be administered on more than 2 consecutive days.

The first dose of the first cycle will require approximately 5 hours in the clinic which include approximately 4 hours of post-dose safety assessments. Subsequent doses will require approximately 3 hours in the clinic which include approximately 2 hours of safety assessments post-dose (see also [Section 1.3, Schedule of Activities \(SoA\)](#)).

No more than 14 days should elapse between cycles. If more than 14 days elapse, the investigator must consult with the medical monitor before initiating the next cycle of treatment. Refer to [Section 6.2](#) for dose modification guidelines and management of toxicities.

Treatment will continue until death, disease progression, unacceptable toxicity, withdrawal of consent, or another reason for withdrawal, or until study discontinuation.

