### 10.3.9 Dose Limiting Toxicity (DLT) Criteria

#### GENERAL PRINCIPLES

A treatment-emergent adverse event (TEAE) will be declared as DLT if both of the following criteria are met:

1. The TEAE occurred after the start of infusion in Cycle 1
  - a. If a TEAE that fulfills a DLT criterion is observed in cycle  $\geq 2$  of Part 3, then the sponsor may declare this event a DLT after consultation with the investigator(s).
2. The TEAE is at least possibly related to MT-3724, as determined by the sponsor after consultation with the investigator(s).

The severity of TEAEs potentially fulfilling the DLT criteria will be graded according to the CTCAE v 5.0.

**POTENTIALLY QUALIFYING TREATMENT-EMERGENT ADVERSE EVENTS:** Any TEAE listed below may represent a DLT for MT-3724 in this study.

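### In Cohort 2, a subject who never received 50 µg/kg in Cycle 1 can still count among the six whose DLTs decide whether Part 4 uses the 50 µg/kg regimen

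*Protocol*

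**What the plan says.** Protocol Section 4.1.1.1 gives two routes to being evaluable in Part 3. One is a DLT after at least one Cycle 1 dose. The other, where toxicity has not delayed or removed doses, is that "subjects have received at least 4 of 6 (67%) doses of MT-3724 within 21 days". Subjects who meet neither are replaced (also Section 7.2).

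Section 6.1.1.2 and Table 6-1 set the Cohort 2 steps: 10 µg/kg on Days 1 and 3, 25 µg/kg on Days 5 and 8, then 50 µg/kg "for the remaining doses (D10, D12) of the first 21-day cycle and all doses of Cycle 2". In Table 6-1 the row "Cycle 1 D10, D12" is the only Cycle 1 row where Cohort 2 differs from Cohort 1 (50 against 25 µg/kg).

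The observation window is in Section 4.1.1: "The DLT assessment period is 21 days. DLTs will be assessed during Cycle 1 of each enrolled dose cohort". The decision rule is in Section 6.1.1.2: "If fewer than 2/6 subjects have a DLT in Cohort 2, then the study will continue to Part 4 using the Cohort 2 dose". Part 4 is planned for at least 88 evaluable subjects (Section 4.1.2).

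The SAP is based on protocol version 7.0 and covers Parts 1 and 2. It has no rule for these cohorts.

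**The concern.** A threshold of four doses in six suits a cycle in which every dose is at the level under test. The SAP describes that setting for Parts 1 and 2 (Section 1.3.1.1), where four of six infusions completed a cycle at one assigned dose. Under step-up dosing, four doses no longer imply exposure to the level being decided on. In Cohort 2 they can be the four that Cohort 1 also receives.

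Cohort 2 tests the step to 50 µg/kg after a Grade 5 capillary leak event at 50 µg/kg in Part 3 (Section 2.2.1). A subject without 50 µg/kg in Cycle 1 adds to the denominator of six but cannot show a 50 µg/kg DLT in the window. With only six subjects, each such case makes it easier to take the higher regimen into Part 4. If the subject goes on, the first 50 µg/kg dose falls in Cycle 2, where Section 10.3.9 leaves it to the sponsor, after consulting the investigators, whether a qualifying event is called a DLT.

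**Working it through.** **The plan's own figure.** 4/6 = 66.7%, which rounds to the stated 67%. It is a share of doses, not of exposure.

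**Exposure (Table 6-1, Cycle 1).**
- Cohort 2, all six doses: 10+10+25+25+50+50 = 170 µg/kg.
- Cohort 2, first four: 10+10+25+25 = 70 µg/kg; 70/170 = 41%.
- Cohort 1, all six: 10+10+4×25 = 120 µg/kg.
- Cohort 1, first four: 70 µg/kg; 70/120 = 58%.

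The least-exposed evaluable, DLT-free Cohort 2 subject therefore matches the least-exposed Cohort 1 subject, and falls below a complete Cohort 1 cycle.

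**Which four-dose patterns lack 50 µg/kg.** Six doses can be reduced to four in 15 ways. If levels follow calendar day, as in Table 6-1, one pattern lacks 50 µg/kg: Days 10 and 12 both missed. If levels follow dose number (first two, next two, remaining), all 15 lack it. Section 6.1.1.2 gives both the dose counts and the days and does not say which governs after a missed dose. The gap exists on either reading. Losing only one dose always leaves at least one 50 µg/kg dose.

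**Effect on the decision rule.** Let *k* of the six evaluable subjects have had no 50 µg/kg. Let *p* be the DLT rate on the full regimen, *q* = 1 − *p*, and *p₀* the rate without 50 µg/kg. The cohort passes with 0 or 1 DLT:
- *k* = 0: q⁶ + 6pq⁵
- *k* = 1: (1−p₀)(q⁵ + 5pq⁴) + p₀q⁵
- *k* = 2: (1−p₀)²(q⁴ + 4pq³) + 2p₀(1−p₀)q⁴

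With p = 1/3:
- *k* = 0: 64/729 + 192/729 = 0.351.
- *k* = 1, p₀ = 0: 32/243 + 80/243 = 0.461. With p₀ = 0.10: 0.9×0.461 + 0.1×0.132 = 0.428.
- *k* = 2, p₀ = 0: 16/81 + 32/81 = 0.593. With p₀ = 0.10: 0.81×0.593 + 0.18×0.198 = 0.516.

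The values of p, p₀ and k are assumptions, since the documents give none of them. Over a range of p (ranges run from p₀ = 0.10 to p₀ = 0):

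| p | k = 0 | k = 1 | k = 2 |
|---|---|---|---|
| 0.20 | 0.655 | 0.696–0.737 | 0.737–0.819 |
| 1/3 | 0.351 | 0.428–0.461 | 0.516–0.593 |
| 0.40 | 0.233 | 0.311–0.337 | 0.408–0.475 |
| 0.50 | 0.109 | 0.172–0.188 | 0.264–0.312 |

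**The case against.** **The case is narrow.** Omissions caused by toxicity fall outside the four-dose route, so they do not create the gap. A subject dosed through Day 8 must then receive nothing more in the cycle, for reasons other than toxicity. After the first three doses, doses need be only 20 hours apart, so there is room to catch up. This stands. The point is about what the rule allows, and its frequency is unknown.

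**A reader might infer that the Day 16 limit forces the 50 µg/kg doses to be dropped.** Table 1-1 says "All 6 doses must be given within the first 16 days". The documents do not support the inference. Section 6.1.1.3 is softer: "All doses should be administered within the first 16 days of the 21-day cycle". The note to Table 1-2 treats a late dose as rescheduled, Section 6.2 allows delays of up to 14 days, and Section 4.1.1.1 counts doses over 21 days. No text says that a late dose is omitted. The gap does not need that premise, because missed visits, a scheduling delay or stopping treatment after the fourth dose are enough.

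**Four-dose subjects are informative.** Section 2.2.1 reports capillary leak at 10 and 25 µg/kg in the combination studies, and the version 11 rationale (Section 12.1) places events within a few days of first dosing or re-dosing. This is fair, and it makes a zero DLT rate without 50 µg/kg optimistic, hence the range up to 10%. Such subjects still say nothing about the step from 25 to 50 µg/kg.

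**Other safeguards exist.** Six is a minimum. The safety management team reviews all available data (Section 4.1.1), the DSMB meets before Part 4 (Section 9.4), and later events may be declared DLTs. These would probably bring a case to light. They are discretionary, none requires 50 µg/kg exposure, and none changes who counts among the six.

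**Conclusion.** The point holds as a gap in the evaluability rule. Nothing in the protocol requires a DLT-free Cohort 2 subject to have received 50 µg/kg in the DLT period before counting towards the decision on 50 µg/kg. The exposure figures (70 of 170 µg/kg, 41%) follow directly from Table 6-1.

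The effect on the decision is illustrative. At an assumed DLT rate of one in three, one unexposed subject moves the chance of passing from 35% to 43–46%, and two move it to 52–59%. Two would be a third of the cohort and should not be taken as expected. The documents do not support saying that the Cohort 2 decision will be wrong, or that such subjects will be common. They support saying that the rule permits it, at the dose where the Grade 5 event occurred, and that closing the gap is cheap.

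**What to change.** Add one sentence to Section 4.1.1.1: *In Cohort 2, a subject without a DLT is evaluable only if at least one 50 µg/kg dose was given in Cycle 1 and the subject was followed to the end of the 21-day DLT period; otherwise the subject is replaced.*

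If levels follow dose number, the minimum Cycle 1 exposure of a DLT-free evaluable subject rises from 70 to 120 µg/kg (10+10+25+25+50). If they follow calendar day, it rises to 95 µg/kg (10+10+25+50).

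Leave the 16-day sentence in Section 6.1.1.3 as it is for this purpose. Stating that doses not given by Day 16 are omitted would remove late 50 µg/kg doses that Section 4.1.1.1 can now count, and so would work against the aim.

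The cost is nothing if no such subject arises. Otherwise it is one replacement subject and about one more 21-day DLT period per case, under the replacement rule already in Sections 4.1.1.1 and 7.2. One limit remains: a first 50 µg/kg dose given late, for example on Day 16, leaves about 5 days of the window, against 11 after a Day 10 dose. The team should weigh that when it reviews the cohort.

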#### **4.1.2      Part 4**

The goal of Part 4 is to provide sufficient evidence to test the null hypothesis that the true response rate with MT-3724  $\leq$  17% vs the alternative hypothesis that the true response rate with MT-3724  $\geq$  32% at the 1-sided alpha level of 0.025 with high statistical power. At least 88 evaluable subjects will be required to test the null hypothesis vs the alternative hypothesis in Part 4. If at least 23 of 88 subjects respond at the end of Part 4, then the null hypothesis is rejected in favor of the alternative hypothesis and the effectiveness of MT-3724 as monotherapy will have been proven. Under the stated null and alternative hypotheses, Part 4 carries 90.4% power at the 1-sided alpha level of < 0.025.

#### **4.1.3      Parts 3 and 4**

All study procedures will be the same for Parts 3 and 4. After eligibility is assessed in the screening period (up to 35 days), subjects enter the treatment period. Each treatment cycle will be 21 days in length. Treatment will continue until death, disease progression, unacceptable toxicity, withdrawal of consent, or another reason for withdrawal, or until study discontinuation. Refer to [Section 6.1.1.4](#) for details regarding treatment beyond progression.

**End of Treatment:** After discontinuation from treatment, all subjects should undergo the End of Treatment (EoT) Visit as soon as possible (up to 14 days) after the last dose of MT-3724 and before start of new therapy.

**Short-term Safety Follow-up:** The Short-term Follow-up (STFU) Visit for safety assessment should occur 30 days ( $\pm$  3 days) after the last dose of MT-3724, except for subjects who withdrew consent and objected to further data collection, started new therapy for DLBCL or started another investigational drug.

**Long-Term Follow-up:** Long-term Follow-up (LTFU) Visits should occur every 3 months ( $\pm$  14 days) after the last dose of MT-3724 for up to 18 months from the last dose. Subjects who discontinue the study for disease progression will be followed only for OS. Subjects with CR, PR, or SD should also be followed for radiology assessment until progressive disease (PD), death, or start of new anticancer treatment.

## 4.2 End of Study

### 4.2.1 End of Study Definition

**Primary Completion:** The primary completion date is defined as the date when the last subject is assessed or receives an intervention for the final collection of data for the primary endpoint(s) for the purposes of conducting the primary analysis. This date is defined as when the last subject has completed all planned assessments for clinical outcomes.

**End of Study (End of trial):** The end of the study is defined as the date of the last visit of the last subject in the study or last scheduled procedure shown in the Schedule of Activities for the last subject in the trial globally.

## 5 STUDY POPULATION

**NOTE:** The investigator or sub-investigator must judge all pre-admission vital signs, physical examination (PE), laboratory or any safety variables to be within normal limits or clinically insignificant. If local standard of care (SoC) procedures or tests were performed prior to signing of the informed consent form (ICF) but are still within 35 days (or 28 days for laboratory safety and radiographic assessments) of the planned dose Day 1, then those results/data can be used for the intended protocol screening procedure. If various parameters within a given procedure are missing from the SoC procedures, then only those missing parameters need to be collected. The medical monitor will also review all screening data to confirm each subject's eligibility prior to dosing initiation. Any laboratory results that exclude study participation may be repeated to confirm accurate exclusion from the study. A subject who is no longer excluded upon retest will be reviewed again by the medical monitor prior to dosing initiation.

In addition, prior to first dose of MT-3724 on Cycle 1 Day 1 (C1D1), the investigator must confirm there have been no changes in the subject's health that would render them medically inappropriate to begin protocol therapy.

Before any study-specific activities/procedures, the appropriate written informed consent must be obtained (see [Section 10.1.4](#)). Prospective approval of protocol deviations to recruitment and enrollment criteria, also known as protocol waivers or exemptions, is not permitted.

## 5.1 Inclusion Criteria

Subjects meeting ALL of the following inclusion criteria will be eligible for participation of the study:

1. Subjects must be informed about the study and fully consent to participation as demonstrated by signing the written ICF before any screening procedure.
2. Male and female subjects  $\geq 18$  years of age at the time of informed consent
3. Subjects must have relapsed or refractory DLBCL according to the Revised European American Lymphoma/World Health Organization classification ([Swerdlow, 2016](#)). Subjects must have proof of CD20+ DLBCL, based on either:
  - a. historical biopsies (obtained with diagnosis of relapsed or refractory disease), or
  - b. fresh biopsies
  - c. bone marrow biopsy, excisional lymph node biopsy, and core biopsy of any involved organ are all acceptable methods; Fine Needle Aspirate is not acceptable.

NOTE: Composite lymphoma (DLBCL and indolent histology in the same specimen) is also acceptable.
4. Subjects must have received at least 2 SoC regimens (including anti-CD20 antibody therapy) appropriate for DLBCL treatment.
  - a. Subjects whose prior therapy includes CAR-T-cell therapy are eligible
  - b. Subjects who underwent stem cell transplant (SCT)  $> 100$  days for autologous SCT or  $> 180$  days for allogeneic SCT before study drug administration.
  - c. Subjects who have been ineligible for SoC DLBCL treatment(s) may be eligible at the investigator's discretion, upon sponsor approval.
5. Subjects must have at least 1 bi-dimensional tumor lesion at screening that is measurable by CT and/or magnetic resonance imaging (MRI) according to the Lugano criteria ([Cheson, 2014](#)). Bi-dimensionally measurable tumor lesion by CT and/or MRI is defined as longest diameter of  $> 1.5$  cm for lymph nodes and  $> 1.0$  cm for extranodal disease.
6. Subjects must have life expectancy of  $> 3$  months from the start of treatment.
7. Subjects must have ECOG performance status of 0-2.
8. Subjects must have met ALL the following laboratory criteria:
  - a. absolute neutrophil count (ANC)  $\geq 1.0 \times 10^9/L$  with no myeloid growth factors (granulocyte colony-stimulating factor [G-CSF] or granulocyte-macrophage colony-stimulating factor preparations) administered within 2 weeks of C1D1
  - b. platelet count  $\geq 50 \times 10^9/L$  with no Thrombopoietin-receptor agonists agents or platelet transfusions given within 2 weeks of C1D1

- c. hemoglobin  $\geq 8.0$  g/dL with no erythropoietin stimulating agents or peripheral red blood cell (PRBC) transfusions within 2 weeks of C1D1
- d. creatinine clearance (CLcr) to be  $\geq 50$  ml/min either measured or estimated using the Cockcroft-Gault formula ([Section 10.2.2.2](#)).
- e. total bilirubin (or direct bilirubin for patients with Gilbert's disease)  $< 1.5 \times$  upper limit of normal (ULN)
- f. alanine transaminase (ALT)  $\leq 3.0 \times$  ULN (or  $\leq 5.0 \times$  ULN if liver involvement).
- g. aspartate aminotransferase (AST)  $\leq 3.0 \times$  ULN (or  $\leq 5.0 \times$  ULN if liver involvement).
- h. international normalized ratio (INR) or prothrombin time (PT)  $\leq 1.5 \times$  ULN (unless on therapeutic anticoagulants)
- i. Activated partial thromboplastin time  $\leq 1.5 \times$  ULN (unless on therapeutic anticoagulants)

9. Have adequate serum albumin, as determined by:

- a. albumin  $\geq 3.0$  g/dL

10. QT interval correction for heart rate using Fridericia's formula (QTcF)  $\leq 480$  ms determined as the average of 3 QTcF values from the triplicate ECG obtained at screening.

11. Women of reproductive potential must have a negative highly sensitive pregnancy test within 72 hours before the start of treatment. Women who are postmenopausal or permanently sterilized (eg, tubal occlusion, hysterectomy, bilateral salpingectomy) may be considered as not of reproductive potential.

12. Subjects of reproductive potential must agree either to abstain continuously from heterosexual intercourse or to use a highly effective birth control method from signing the informed consent until the STFU visit for females and until 90 days after the last dose of MT-3724 for males. Refer to [Section 10.4](#) for guidance on contraception.

13. Subject must be able to comply with all study-related procedures and medication use.

